13.3 Analysis Populations

The analysis populations include the following:

- The intention-to-treat (ITT) population will consist of all randomized patients. The ITT population is the primary population for the efficacy analysis.
- The safety population (SAF) will include all patients who received at least one dose of trial medication. This population will be used for safety analyses.
- The per-protocol (PP) population will consist of all ITT patients who received at least one dose of trial medication and without major protocol deviations as defined in the statistical analysis plan and finally decided in a Data Review Meeting before database lock. This population will be utilized to evaluate the sensitivity of the primary efficacy analysis.
- The pharmacokinetic (PK) population will consist of all randomized patients including the subset of patients who had blood samples collected for PK noncompartmental profiling, who had at least one measureable CetuGEX™ antibody concentration.

In the event that a patient is randomized incorrectly or is administered the incorrect study medication, analyses of the ITT population will be based on the assigned treatment whereas all other analyses will be based on the actual treatment.

13.4 Statistical Analyses

13.4.1 General Methods

For dichotomous and categorical variables, absolute and relative frequencies (counts and percents) will be calculated. For continuous variables, comprehensive data summaries will be presented with sample characteristics (n, arithmetic mean, standard deviation, minimum, lower quartile, median, upper quartile and maximum) by treatment. Where data are collected over time, both the observed data and the change from baseline will be summarized at each visit.

13.4.2 Study Patients and Demographics

13.4.2.1 Disposition and Withdrawals

The numbers of patients randomized, completing, and withdrawing, along with reasons for withdrawal, will be tabulated overall and by treatment group. The number of patients in each analysis population will be reported. This analysis will be based on all patients.

13.4.2.2 Demographics and Other Baseline Characteristics

Demographic variables will include age, race, weight, BMI, smoking status and alcohol consumption.

Other baseline characteristics will include:

- Tumor specific medical history (time since first diagnostic, tumor pre-treatment, tumor grading)
- FcγRIIIa status
- General medical history
- Prior and concomitant medications will be summarized by treatment group and by the number and percentage of patients taking each medication, classified using World Health Organization Drug Dictionary (WHO-DD).

These analyses will be conducted for the safety population.

13.4.3 Efficacy Analyses

13.4.3.1 Primary Analysis

Primary endpoint of the trial is PFS defined as time from randomization until disease progression (assessed by the investigator) or death of any cause. The PFS time will be censored at the time of the last tumor assessment if the patient is alive and without progression at the last time of observation.

The primary efficacy analysis for PFS will be based on the ITT population. A log-rank test will be used to test the null hypothesis of equal treatment effects at an overall significance level of 0.05. The primary efficacy analysis will not be stratified by the

factors used for stratification at randomization in order to preserve the estimated power considering the high number of strata. As a sensitivity analysis, a proportional hazards regression model will be applied and the effects of the stratification factors, the p16 status, and the EGFR status will be estimated:

- FcγRIIIa status (FF or FV or VV),
- p16 status (+/-),
- EGFR status (+/-),
- Oral cavity and oropharynx vs. other locations,
- Locally recurrent vs. metastatic disease.
- EGFR treatment naïve vs. EGFR treatment as part of multimodal treatment.

The Kaplan-Meier method will be used to estimate the survival functions. Median survival times together with their 95%-confidence intervals will be retrieved from the survival functions.

The analysis will be repeated for the PP population as a sensitivity analysis.

13.4.3.2 Secondary Analyses

A Chi-squared test will be performed to evaluate the effects of treatment on response rates as defined in Section 13.1.2. A logistic regression model will be fit to estimate odds ratios for the association of stratification factors, the p16 status, and the EGFR status with response categories. Corresponding 95%-confidence intervals will be calculated for the treatment differences in response rates.

Overall survival and TTF will be analyzed analogously to PFS on an ITT basis. Additional models will be applied to evaluate the impact of second line treatments on OS. Details will be given in the SAP.

If subgroup sample sizes allow, analyses of the primary and secondary efficacy endpoints will be repeated for the FcγRIIIa-allotype subgroups (i.e., FF, FV, VV), the p16 status subgroups as well as the EGFR status subgroups, omitting the FcγRIIIa factor, the p16 status and the EGFR status factor, respectively.

13.4.3.3 Pharmacokinetics

The PK samples will consist of 2 groups; samples from the PK profile group and samples from all patients of the CetuGEX™-arm before and at the end of each infusion (up to the 10th infusion). The samples from the PK profile group will be used for non-compartmental analyses. All samples will be pooled for a population PK analysis estimating clearance and volume of distribution. Both results from PK methods of analysis will be reported as they have different strengths and weaknesses.

The population PK analysis will be described in a separate population PK plan that follows recommendations from regulatory guidance from FDA (Guidance for Industry – Population Pharmacokinetics) and EMA (Guideline on reporting the results of population pharmacokinetic analyses CHMP/EWP/185990/95, June 2007). These regulatory

guidance will also be followed for conduct of the population PK analysis with validation by boot-strapping techniques and reporting results. Population PK analysis will be conducted using Pharsight Phoenix NLME[®] software or other established population PK software such as NONMEM[®].

These analyses will be conducted for the PK population.

13.4.4 Safety and Tolerability Analyses

The safety analysis will be performed for the safety population.

13.4.4.1 Adverse Events

Adverse Events will be coded using the Medical Dictionary for Regulatory Activities (MedDRA). Summaries of incidence rates (frequencies and percentages) of individual TEAEs by MedDRA System Organ Class and Preferred Term will be prepared. Such summaries will be displayed for all TEAEs, TEAEs by maximum intensity and TEAEs by strongest relationship to study treatment.

Treatment emergent adverse events (TEAEs) are defined as any AE which started or deteriorated at or after start of treatment. Incidences for TEAE will be calculated on Preferred Term level, on System Organ Class level and globally by treatment group. On each analysis level, a patient will be counted only once. Frequencies for TEAE will also be given for causality and severity graded according to NCI-CTC (AE criteria Version 4.0).

In addition, toxicity as evaluated via incidence of AEs will be analyzed by FcγRIIIa allotype subgroups (FF, FV and VV).

The incidences of ADA will be summarized in frequency tables per treatment arm.

13.4.4.2 Clinical Laboratory Evaluations

For hematology and biochemistry variables, descriptive summaries of observed values and changes from baseline will be presented by treatment arm.

Each abnormal value will be flagged to show whether it is a value below or above the reference range. For the assessment of laboratory variables, 5 categories will be used that take into account the investigator's assessment of clinical relevance: "clin. rel., above", "non-clin. rel., above", "within", "non clin. rel., below", "clin. rel., below".

The assessments of laboratory variables concerning reference ranges and clinical relevance will be tabulated by visit for each clinical laboratory parameter by treatment arm (frequency tables). Additionally, for each laboratory parameter, shifts in assessments from baseline to the last on-study value will be presented by treatment arm (shift tables).

Laboratory values that are outside the reference range will also be flagged in the data listings, along with corresponding reference ranges.

The assessment of categorical urinalysis variables will be tabulated by visit for each urine parameter by treatment arm (frequency tables). Additionally, for each of these urine

parameter shifts in assessments from baseline the last on-study value will be presented for each treatment arm (shift tables).

13.4.4.3 Vital Signs

Descriptive summaries of observed values and changes from baseline will be calculated for vital signs. These summaries will be presented by visit and treatment arm.

13.4.4.4 Electrocardiograms and Echocardiograms

Descriptive summaries of observed values and changes from baseline will be calculated for ECG variables. QT will be corrected according to Bazett. Frequency and shift tables will be presented for the classified values of QT_c as given by the International Conference on Harmonisation (ICH)-E14, as well as for the overall clinical assessment.

For ECHO/MUGA assessments, descriptive values of observed values at baseline (“Normal”/“Abnormal [not] clinically significant”) will be presented by treatment arm.

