---------------------	---

	
each analysis level, a patient will be counted only once. Frequencies for TEAE will also be given for causality and severity graded according to Common Toxicity Criteria (NCI-CTC; AE criteria Version 4.0). In addition, toxicity as evaluated via incidence of AEs will be analyzed by Fc-gamma receptor allotype subgroups (FF, FV, VV) The incidences of ADA will be summarized in frequency tables per treatment arm.
 
For biomarkers as well as hematology and biochemistry laboratory variables, descriptive summaries of observed values and changes from baseline will be presented by treatment arm. The assessments of laboratory variables concerning reference ranges and clinical relevance will be tabulated by visit for each clinical laboratory parameter by treatment arm (frequency tables). Additionally, for each laboratory parameter, shifts in assessments from baseline to the last on-study value will be presented by treatment arm (shift tables).
 
Descriptive summaries of observed values and changes from baseline will be calculated for vital signs. These summaries will be presented by visit and treatment arm.
 
Descriptive summaries of observed values and changes from baseline will be calculated for ECG variables. QT will be corrected according to Bazett. Frequency and shift tables will be presented for the classified values of QT_c as given by the International Conference on Harmonisation (ICH)-E14, as well as for the overall clinical assessment.
 
Finding in post-baseline physical examinations will be documented as AE and analyzed as part of the general AE analysis.

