10.3.6.2 Clinical Examinations

Clinical examinations will be performed at different time points as outlined in the previous sections and in the schedule of visits (see Sections 10.1 and 18.1).

Vital Signs

Vital signs, including heart rate, diastolic and systolic blood pressure and body temperature, will be measured at every study visit prior to infusion after the patient has been at rest in a sitting position for at least 5 minutes.

Eastern Cooperative Oncology Group Performance Status

The ECOG performance status will be recorded at each visit where study medication was administered, during combination treatment phase and single agent maintenance phase, at the Safety Visit and at the Final Examination. The performance status grades and corresponding descriptions are given in Appendix A.

Electrocardiogram

A standard 12-lead ECG will be performed at scheduled time points after the patient has been supine for at least 5 minutes. The QT interval (defined as the time period from earliest onset of the QRS complex to the latest offset of the T wave in the same lead; the lead with the longest QT interval should be selected) has to be exactly measured. All ECG recordings will be identified with the patient number, date and time of the recording and data including 3 selected consecutive QT intervals will be entered into the patient's eCRF. Original ECG records will be kept in the patient's file. Copies will be filed in the Investigator's File.

In case of any clinically relevant abnormalities, these should be reported as AEs (see Section 11).

ECHO/MUGA

An echocardiogram or a MUGA scan will be performed at screening. All the recordings will be identified with the patient number, date and time of the recording and data will be entered into the patient's eCRF. Original records will be kept in the patient's file. Copies will be filed in the Investigator's File.

Physical Examination

A complete physical examination will be performed at screening, at each day of study drug administration, and at the Safety Visit, based on the following body systems: general appearance, head (eyes/ears/nose/throat), respiratory, cardiovascular, abdomen, urogenital, musculoskeletal, neurological, lymph nodes and skin.

Body weight, height and BMI will be measured as part of the demography assessments, and body weight will also be measured on further scheduled time points for safety assessments.

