### 10.4 Electrocardiogram

The summary ECG assessment (categories: normal, abnormal – not clinically significant, abnormal – clinically significant) will be tabulated by visit (frequency tables). Additionally, shifts in assessments from baseline to EOS visit will be presented by treatment arm (shift tables).

Descriptive summaries of actual values and changes from baseline will be presented for ECG measures of PR interval, QRS interval, QT interval, QTc interval (Bazett), and HR (heart rate) by visit and treatment arm.

If not available in the clinical database, Bazett's Correction (QTcb) will be derived as follows:

$$\text{Bazett's Correction (QT}_{c_b}\text{)} \quad \text{QT}_{c_b} = \frac{QT_{msec}}{\sqrt{RR}}$$

where: Relative Rate:  $RR = 60 / \text{HR}$   
HR = heart rate obtained from ECG.

Also, the number and percentage of patients in each treatment group with QTc values 451 - 480 ms, 481 - 500 ms or >500 ms and the number and percentage of patients in each treatment group who experienced a change >30 ms or a change >60 ms will be presented by visit.

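### Bazett is the only QT correction, so the 451-480 ms class and the >30 ms change count depend on heart rate; the promised QTc-class shift table is also missing from the SAP

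*Protocol*

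**What the plan says.** The protocol synopsis and protocol 13.4.4.4 both name Bazett ("QT will be corrected according to Bazett") and no other correction. SAP 10.4 summarises "ECG measures of PR interval, QRS interval, QT interval, QTc interval (Bazett), and HR (heart rate) by visit and treatment arm", as values and as changes from baseline. Where QTc is not already in the database, the SAP derives it as QT divided by the square root of 60/HR, with "HR = heart rate obtained from ECG". The classes are "QTc values 451 - 480 ms, 481 - 500 ms or >500 ms". The SAP also counts patients "who experienced a change >30 ms or a change >60 ms will be presented by visit"; these change thresholds do not appear in protocol 13.4.4.4.

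On recording conditions, protocol 10.3.6.2 says: "A standard 12-lead ECG will be performed at scheduled time points after the patient has been supine for at least 5 minutes". Protocol 10.1.3 places the Cycle 3 and Cycle 5 ECGs before dosing.

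On shift tables, the protocol says: "Frequency and shift tables will be presented for the classified values of QT_c". SAP 10.4 plans a shift table only for the overall ECG assessment (normal, or abnormal with or without clinical significance).

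**The concern.** Bazett divides by a square root. If QT shortens with heart rate more slowly than that, the corrected value still rises with heart rate. A patient whose heart rate increases after baseline can then move into a higher class, or pass a change threshold, with no change in repolarization.

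At stake is how the categorical QTc tables read. If heart rate differs between arms, the difference appears as a drug effect on QTc. If it does not, both arms carry similar false outliers, and a real difference is harder to see against them. By-visit tables also do not show how many patients ever moved up a class, which a shift table to the worst post-baseline class would show.

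**Working it through.** The documents give no QTc result to reproduce. All heart rates, QTc means and SDs below are assumptions.

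**1. Formula.** From SAP 10.4, QTcB = QT/(60/HR)^(1/2). This is standard Bazett with the RR interval in seconds. The cube-root form is QTcF = QT/(60/HR)^(1/3).

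**2. Ratio.** QTcB/QTcF = (HR/60)^(1/6).

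| HR (bpm) | Ratio | QTcB if QTcF = 410 ms |
|---|---|---|
| 60 | 1.000 | 410 |
| 70 | 1.026 | 421 |
| 80 | 1.049 | 430 |
| 90 | 1.070 | 439 |
| 100 | 1.089 | 446 |

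**3. Heart rate at which Bazett alone reaches a class.** HR = 60 × (threshold/QTcF)^6.

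| QTcF (ms) | reaches 451 ms | reaches 481 ms | reaches 501 ms |
|---|---|---|---|
| 400 | 123 bpm | 181 | 232 |
| 420 | 92 | 135 | 173 |
| 440 | 70 | 102 | 131 |

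For a change t at constant QTcF of 420 ms, the heart rate needed is 60 × ((HR0/60)^(1/6) + t/420)^6. A 30 ms rise needs 60 to 91, 70 to 105 or 80 to 119 bpm. A 60 ms rise needs 60 to 134, 70 to 153 or 80 to 172 bpm.

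**4. Share above 450 ms.** Simulation with QTcF normal (mean 410, SD 18), HR normal (SD 14) and independent of QTcF. By Fridericia the share is 1 − Φ(40/18) = 1.3%. By Bazett:

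| Mean HR (bpm) | >450 ms |
|---|---|
| 70 | 9.5% |
| 75 | 13% |
| 85 | 23.5% |
| 95 | 36% |

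At mean HR 85, only 2.0% exceed 480 ms and 0.17% exceed 500 ms by Bazett. So about 23.5 − 2.0 = 21.5% fall in the 451-480 ms class.

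**5. Change from baseline.** Baseline HR mean 80 (SD 12), HR change mean +10 (SD 10), no drug effect. The mean Bazett change is about +8 ms. The result depends on the assumed within-patient SD of the QTcF change:

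| SD of QTcF change | >30 ms, Bazett | >30 ms, Fridericia |
|---|---|---|
| 10 ms | 5.5% | 1 − Φ(3) = 0.1% |
| 20 ms | 17% | 1 − Φ(1.5) = 6.7% |

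With SD 10 and no mean rise in heart rate, Bazett gives 1.4%. For a change above 60 ms, Bazett gives under 0.01% at SD 10, and 1.3% against 0.1% at SD 20.

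**6. If the cube root is not exact.** With a true exponent of 0.40 the excess factor is (HR/60)^0.10. At 80 bpm and a true QTc of 410 ms the over-correction is 12 ms instead of 20 ms, about 60% as large.

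**7. Shift tables.** Protocol 13.4.4.4 promises both frequency and shift tables for the QTc classes. The SAP table list has 14.3.5.2.2 (shift in the overall assessment), 14.3.5.2.5 (QTc classes by visit) and 14.3.5.2.6 (QTc change classes by visit). None is a shift table of QTc class, yet SAP section 12 declares full agreement with the protocol. This point needs no assumption.

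**The case against.** Bazett is pre-specified and the tables are descriptive: no test, decision rule or stopping rule uses QTc. The trial is randomized 1:1 with the same chemotherapy in both arms, so without an arm difference in heart rate both arms are inflated alike. Uncorrected QT and heart rate are summarised by visit and arm, so a reader can see whether heart rate rose or differed. Clinically relevant ECG abnormalities are also reported as adverse events.

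Most of this stands and keeps the point small. Two parts do not fully answer it. Summaries of QT and heart rate reveal an artefact in the means but do not reclassify individual patients. Equal heart rates in the two arms are not assured either: under protocol 9.3 premedication at later infusions differs by arm, though the documents do not say whether that affects heart rate.

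A reader might infer that raised heart rates are expected in these patients and that the QTc classes and both change thresholds will largely reflect heart rate. The documents do not support that. No section gives an expected heart rate, ECGs are taken supine after rest, those in Cycles 3 and 5 are pre-dose, and significant arrhythmia and hemoglobin below 9 g/dl are excluded at entry. The arithmetic also limits it: heart rate alone needs 131 bpm or more to reach 501 ms when QTcF is 440 ms or lower.

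**Conclusion.** The point holds in limited form. Bazett alone makes the 451-480 ms class and the >30 ms change count sensitive to heart rate. The >500 ms and >60 ms categories are little affected in absolute terms at plausible resting rates.

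The direction follows from the SAP's formula if QT shortens with heart rate more slowly than the square root. The size rests on assumed heart rates and QTc spread. The excess above 450 ms is present at an ordinary mean of 70 bpm, so it does not require raised heart rates. The contrast for changes above 30 ms is less stable: about 40-fold (5.5/0.14) if the SD of the QTcF change is 10 ms, but 2.6-fold (17.2/6.7) if it is 20 ms. Bias between arms is conditional on an arm difference in heart rate, which the documents neither predict nor rule out.

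The missing QTc-class shift table is a plain discrepancy between protocol and SAP. Neither issue touches the primary endpoint or the sample size.

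**What to change.** In protocol 13.4.4.4 (and the matching synopsis text) and SAP 10.4, also derive QTcF = QT/(60/HR)^(1/3) from the recorded QT and ECG heart rate. Present the same summaries, classes and change thresholds with it, and keep the pre-specified Bazett tables alongside. State where any QTc value already in the database comes from, since the SAP derives Bazett only when none is available.

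Separately, add to SAP 10.4 and its table list the QTc-class shift table that the protocol promises. State its post-baseline reference, which the protocol leaves open; the worst post-baseline class per patient is one option. Otherwise record the omission in SAP section 12.

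The cost is one derived variable and a few extra descriptive tables, with no new data or visits. The drawback is a second set of QTc tables that may disagree with the first, so the SAP should say in advance how the two will be read together.

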13.4.4.5 Physical Examination Findings

Findings in post-baseline physical examinations will be documented as AE and analyzed as part of the general AE analysis.

13.4.5 Interim Analysis

No formal interim analysis will be performed. Descriptive summaries of PFS and OS events, including point estimates and 95% confidence intervals of the hazard ratios, will be provided to the DSMB at all meetings starting from the second meeting (approximately 9 months after start of enrollment) in order to monitor potential detrimental effects of the investigational compound.

14 STUDY CONDUCT

Steps to ensure the accuracy and reliability of data include the selection of qualified investigators and appropriate study sites, review of protocol procedures with the investigator and associated personnel prior to the study, periodic monitoring visits, and meticulous data management.

14.1 Sponsor and Investigator Responsibilities

14.1.1 Sponsor Responsibilities

The Sponsor is obligated to conduct the study in accordance with strict ethical principles (Section 16). The sponsor reserves the right to withdraw a patient from the study (Section 8.3), to terminate participation of a study site at any time (Section 14.6), and/or to discontinue the study (Section 14.5.2).

Glycotope GmbH agrees to provide the investigator with sufficient material and support to permit the investigator to conduct the study according to the study protocol.

